9.2. RANDOMIZATION

The randomization list will be generated with a computer procedure by a CRO independent statistician not involved in the conduct of the study and will be provided to Dompé in a sealed envelope to prevent unblinding. The facility responsible of IMP packaging/labelling will also receive appropriate randomization codes for the purpose of IMP preparation.

Randomization will be stratified by site to ensure balanced assignment across treatment groups. A master randomization list will be generated, randomizing an excess of patients to allow competitive recruitment within each center.

Access to individual patient treatment code will be allowed only in the event of a medical emergency where the knowledge of patient treatment is required to provide the patient with appropriate care. The investigator and Dompé Pharmacovigilance will have access to the randomization code for a specific patient in case of a medical emergency or for safety reasons. Unblinding events will be recorded and reported in the Clinical Study Report ([CSR](#)). The treatment assignment information will be kept confidential and will not be disclosed to any other.

Once the study has been completed and the database has been locked, the treatment assignment information will be accessible to the study biostatistician(s) who will perform the statistical analyses and will generate reports.

9.3. ANALYSIS POPULATION

The following population will be defined:

- The Safety ([SAF](#)) population will consist of all randomized patients who received at least one dose of the investigational product. Safety population will be analyzed according to the actual treatment received. The SAF population will be used to present results on safety data.
- The Full Analysis Set ([FAS](#)) population will consist of all randomized patients who received at least one dose of the investigational product. FAS population will be analyzed according to the intention-to-treat ([ITT](#)) principle. The FAS population will be used for the primary analysis of the study and to present results on efficacy data.

9.4. STATISTICAL METHODOLOGY

Statistical analysis will be performed by the CRO appointed by Dompé.

All patient data collected during the study will be listed by patient.

Summary statistics appropriate to the distribution of the primary variable will be calculated separately by treatment arm.

For continuous data, number of observations, mean, standard deviation, median and range (minimum and maximum) will be presented. For qualitative data, frequency distributions and percentages per category will be presented. If appropriate, confidence intervals around the mean or the proportions will be presented.

Unless otherwise specified, the significance level for statistical testing will be 0.05 and two-sided tests.

The Statistical Analysis Plan (SAP) will be issued before database lock with more technical and detailed elaboration of the principal features of statistical analyses. Additional post-hoc analysis may be produced to further allow comparison between ladarixin and placebo, according to the results obtained.

Any deviations from the original statistical plan (including unplanned analyses) will be clearly documented in the CSR.

9.4.1. Demographic and baseline characteristics

Demographic and baseline characteristics will be summarized for all patients in the FAS population, by treatment group.

9.4.2. Analysis of efficacy variables

9.4.2.1. Primary analysis

The following null hypothesis is defined: the proportion of patients with an HbA1c reduction from baseline of $\geq 0.50\%$ (absolute difference) without episodes of severe hypoglycemia (level 3) at week 27/28 (visit 4) in ladarixin group is lower or equal than control:

$$H_0: T_{\text{LADARIXIN}} \leq T_{\text{CONTROL}}$$

$$H_1: T_{\text{LADARIXIN}} > T_{\text{CONTROL}}$$

where $T_{\text{LADARIXIN}}$ and T_{CONTROL} are the proportions of patients with an HbA1c reduction from baseline of $\geq 0.50\%$ without episodes of severe hypoglycemia for ladarixin and control groups, respectively. The null hypothesis H_0 will be rejected, and superiority of ladarixin declared if primary analysis p-value will be lower than 0.05.

Primary endpoint will be analyzed by means of a logistic regression model, adjusting for treatment, stratification factor and other baseline characteristics that will be defined in the SAP. A one-sided test will be used to test for differences between treatment groups.

Summary statistics appropriate to the distribution of the primary variable will be calculated separately by treatment arm.

9.4.2.2. Secondary analyses

Analyses will be performed on all secondary CCI endpoints at each available time point by means of descriptive statistics and by appropriate inferential tests, depending on the nature of the variable and its distribution. Data transformation might be used in order to satisfy the assumption of normality requested by parametric statistical tests. In case such assumptions are not met, non-parametric counterpart tests will be used. Details will be provided in the SAP.

The proportion of responders assessed at week 11/12 (visit 3) will be analyzed using the same strategy of the primary endpoint.

9.4.2.3. Analysis of safety variables

TEAEs, ADRs and TESAEs will be presented by treatment arms in terms of number of TEAEs and incidence by System Organ Class and Preferred Term using MedDRA. Analyses will be provided also by severity and relationship to the study drug.

Vital signs and safety laboratory tests will be presented using descriptive statistics at each available visit. Additionally, the frequency of subjects reporting an abnormal or abnormal clinically significant laboratory value will be presented for each laboratory parameter.

9.4.3. Intermediate analyses for the DMC

Safety data will be reviewed on an ongoing basis by a Data Monitoring Committee (DMC). Full details of the activities and responsibilities of the DMC are provided in the study DMC Charter (see additional details in [Section 12.6](#)).

The DMC will give careful consideration to the appropriateness of trial continuation if there is emerging evidence that ladarixin is harmful. Since the DMC does not monitor primary endpoints for early efficacy termination, no Type I error adjustment is necessary. Anyhow, access to unblinded information on the primary analyses is allowed in order to balance patient safety risk against a possible gain in efficacy.

9.4.4. Specification of subgroups for analysis

Sub-group analyses of efficacy endpoints will be performed ad hoc (e.g. subgroup of patients defined by age, HbA1c value, BMI etc.), according to the results obtained in the whole population. Statistical details on subgroup analysis will be reported in the CSR.

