9.1. SAMPLE SIZE

Sample size calculation was based on results obtained in the phase 2 trial with ladarixin in T1D onset. Considering the following assumptions:

- randomization ratio 1:1 (ladarixin: placebo),
- one-side type I error of 0.05,
- expected difference in favor of ladarixin in terms of responders: ~22.5%, and
- power of 80% to detect the expected treatment effect

a total of 76 evaluable patients are required; to account for a possible 10% of patients not evaluable for the primary variable after enrollment, up to 86 patients will be enrolled.

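### Section 9.4.4 lets the whole-population results decide which efficacy subgroups are analysed, which weakens the interpretation of any subgroup finding

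*Protocol*

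**What the plan says.** Section 9.4.4 of the protocol states: "Sub-group analyses of efficacy endpoints will be performed ad hoc (e.g. subgroup of patients defined by age, HbA1c value, BMI etc". It goes on to say that this is done "according to the results obtained in the whole population. Statistical details on subgroup analysis will be reported in the CSR". Age, HbA1c and BMI are examples in an open list.

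Section 9.4 adds a similar permission for the trial as a whole: "Additional post-hoc analysis may be produced to further allow comparison between ladarixin and placebo, according to the results obtained". It also contains a disclosure rule: "Any deviations from the original statistical plan (including unplanned analyses) will be clearly documented in the CSR".

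On timing, Section 9.4 says: "The Statistical Analysis Plan (SAP) will be issued before database lock". Sections 5.1.4 and 9.2 break the blind and release treatment assignments to the analysing statisticians only after lock.

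On significance levels, Section 9.1 uses a "one-side type I error of 0.05" and Section 9.4.2.1 says of the primary endpoint: "A one-sided test will be used to test for differences between treatment groups". For everything not otherwise specified, Section 9.4 says "the significance level for statistical testing will be 0.05 and two-sided tests". Section 9.4.4 sets no level or sidedness of its own.

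**The concern.** A protocol may leave subgroup details to the SAP, and silence here would be no finding. Section 9.4.4 is not silent. It states a selection rule, and the rule is the overall result. Elsewhere the protocol names the SAP when it defers detail: covariates in 9.4.2.1, secondary tests in 9.4.2.2, sensitivity analyses in 9.4.5. Here it names the CSR.

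When the choice of factors follows the data, a nominal subgroup p-value no longer has its usual meaning, because the reader cannot tell how many looks were taken. Writing the rule into the protocol also blurs the line between planned and unplanned work: a subgroup picked after unblinding could be presented as provided for by the protocol.

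Phase II findings inform later designs. In this programme, Section 2.5.2 reports an earlier new-onset trial whose primary analysis was not significant (p=0.3303), while an HbA1c and hypoglycemia responder outcome was (p=0.0248). Section 9.1 bases the present sample size on that trial. The responder outcome was an endpoint, not a subgroup, but the example shows why results outside a failed primary analysis need a clear status.

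**Working it through.** **Can the rule be carried out in the SAP?** The SAP is issued before lock (9.4), and treatment codes become available after lock (5.1.4, 9.2). The natural reading of results in the whole population is the overall treatment comparison, which does not exist until after lock. A choice that follows those results therefore comes after the SAP. A SAP that fixed the subgroups would be good practice, but it would depart from 9.4.4 as written.

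**How much does it matter?** The protocol gives no figure for subgroups, so there is none to reproduce.

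Inputs from the protocol:
- 76 evaluable patients, 1:1, so 38 per arm (9.1)
- three named example factors (9.4.4)
- one-sided 0.05 for the primary test (9.4.2.1) and two-sided 0.05 as the default (9.4)

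Assumptions:
- each factor is split about 50:50, independently of the others
- an unadjusted pooled two-proportion z-test is run in each half
- the responder rate is 10%, 20% or 30% in both arms (the protocol states no control rate)
- only the primary endpoint is examined

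*Rough guide, treating the tests as independent.* P(at least one) = 1 − (1 − α)^k, with k two halves per factor.
- Three factors, k = 6: 1 − 0.95^6 = 26.5%; in the favourable direction of a two-sided test, 1 − 0.975^6 = 14.1%.
- Five factors, k = 10: 1 − 0.95^10 = 40.1%; 1 − 0.975^10 = 22.4%.

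These overstate the chance, because halves defined by different factors share patients and because the case of interest is a non-significant primary test.

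*Simulation under no drug effect, given a non-significant primary test.* Chance of at least one favourable significant half, at responder rates of 10 / 20 / 30%:

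| Factors | z > 1.645 (one-sided 0.05) | z > 1.960 (two-sided 0.05, favourable side) |
|---|---|---|
| 1 | 6.1 / 6.8 / 6.6% | 1.9 / 2.8 / 2.8% |
| 3 | 15.0 / 16.7 / 16.3% | 5.1 / 7.5 / 7.5% |
| 5 | 20.9 / 23.4 / 22.3% | 7.9 / 11.4 / 11.1% |
| 10 | 31.0 / 34.0 / 32.6% | 12.9 / 18.6 / 18.1% |

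A separate simulation with all 86 patients (43 per arm) gave 15.5 / 16.3 / 16.7% for three factors and 21.3 / 22.7 / 22.4% for five at one-sided 0.05, so the number evaluable hardly matters.

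*More endpoints.* Section 9.4.4 covers efficacy endpoints in the plural. Counting Section 7.1 by visit gives responders 2, HbA1c change 2, insulin requirement 2, and five CGM measures at two visits 10, for a total of 16. Treating these as normal variables with a common correlation of 0.3 to 0.7 (assumed), three factors give at least one favourable significant result in 59-84% of trials one-sided and 40-66% two-sided. With four variables the ranges are 38-49% and 23-30%.

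*Information in one half.* 76 / 4 = 19 patients per arm. For the assumed difference of about 22.5 points, one-sided power there is 55.5% at a control rate of 7.5%, falling to 40.4% at 30%. Single subgroup results will be imprecise in either direction.

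**The case against.** The strongest reply is that the harm is bounded and partly disclosed already. Section 9.4.2.1 ties the declaration of superiority to the primary p-value alone, so no subgroup can rescue the trial under the stated rule. Section 9.4.4 openly calls the analyses ad hoc, and Section 9.4 requires unplanned analyses to be documented in the CSR. Exploratory subgroup work in phase II is legitimate. All of this stands. But documentation discloses selection without removing it, and an analysis that 9.4.4 has authorised may not be counted as unplanned.

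Stronger readings that a reader might infer are not supported:
- *A spurious subgroup is likely after a failed primary analysis.* On the primary endpoint with three to five factors the chance is well below one half, and about 5-12% at the two-sided default. It passes one half only when many endpoints are searched under assumed correlations.
- *Subgroups will be specified only in the CSR.* The text says that details will be reported there. The unseen SAP could still name some.
- *Within-subgroup p-values will be used.* The protocol never says so; they are an assumption of the calculation. Cut-points and the choice of test are commonly left to the SAP, and their absence is not part of this point.
- *One-sided 0.05 is the subgroup level.* A subgroup of the primary endpoint might inherit it, but on the plain text the two-sided default applies. Both are therefore shown.

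**Conclusion.** The point holds in limited form. Section 9.4.4 fixes a poor rule: it makes the choice of efficacy subgroups follow the unblinded overall results and authorises this in advance. The primary analysis and its type I error are untouched.

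For three to five factors on the primary endpoint, the chance of a false favourable subgroup after a non-significant primary test is about 16-22% one-sided or 5-12% two-sided. With three factors that is about three times the nominal 5% one-sided, and two to three times the 2.5% favourable tail of a two-sided test. These figures rest on 50:50 splits, unadjusted within-half tests, null responder rates of 10-30% and no drug effect. Free cut-points, further factors or further endpoints would raise them. The change is worth making because it is cheap and protects the reading of the results, not because the main conclusion is at risk.

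**What to change.** Replace Section 9.4.4 with a rule that does not depend on the results:
- Name a short list of baseline factors, for example HbA1c, BMI and age, which are already collected, and fix their cut-points in the SAP before unblinding.
- Assess each by a treatment-by-factor interaction in the primary logistic model. If a formal family-wise level is wanted for three factors, 0.05 / 3 = 0.0167 each keeps the total at or below 0.05.
- Report all listed subgroups, with estimates and confidence intervals, whatever the overall result.
- Label any other subgroup post hoc and hypothesis-generating, and apply the same label to the further analyses permitted in Section 9.4.

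The cost is one paragraph in the protocol and a matching one in the SAP, with no new data. Interaction tests will have little power at this sample size, so the intervals should carry the interpretation. The sponsor gives up presenting result-driven subgroups as planned; post hoc exploration remains possible.

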9.4.5. Missing data

All reasonable efforts will be made to reduce the rate of missing data. Investigators will be trained about the importance of patient retention and full data capture. Also, any reasonable attempts should be made by the Investigators to emphasize continued patient's participation for the full duration of the trial. However, in order to minimize missing data, if a patient cannot refer to the site for a planned follow-up visit, the Investigator will try to obtain any relevant information from the patients, including documents/laboratory results available from local medical care.

The number of subjects with missing data will be presented under the "Missing" category. Missing values will not be included in the denominator count when computing percentages. When continuous data will be summarized, only the non-missing values will be evaluated for computing summary statistics.

For the primary analysis, since patients who discontinue the IMP will not be withdrawn from the study but will be asked to complete safety and efficacy assessments as per the protocol, missing data due to intercurrent events will be addressed by using multiple imputation based on retrieved dropouts information. Retrieved dropout patients are defined as patients who discontinue study treatment and decide to remain in the study by following the schedule of assessments and continuing to adhere to protocol requirements. If not enough data were retrieved after study treatment discontinuation to assure the convergence of the MI-RD regression model (the final decision will be done at the time of the analysis and reported in the CSR), the same multiple imputation model will be fit using data from subjects of control group, washing-out the effect of treatment. This approach does not assume benefits for ladarixin in case of discontinuation and limits a post-discontinuation clinical effect to that of placebo. Specific sensitivity analyses will be defined in the SAP to assess the robustness of results on primary endpoint versus assumptions used in the statistical model for the main estimator.

10. ETHICAL CONSIDERATIONS

10.1. INDEPENDENT ETHICS COMMITTEE (IEC) / INSTITUTIONAL REVIEW BOARD (IRB)

It is the responsibility of the CRO appointed by Dompé or of the Study PI (US site) to obtain approval of the trial protocol/amendments from the appropriate IEC/IRB.

Prior to the initiation of the study, the followings will be submitted to the IEC/IRB for approval:

- the study protocol,
- the ICF,
- the current version of the Investigator's Brochure,
- Investigator's current curriculum vitae (CV) as well as the current CVs of all key study personnel,
- any other requested document(s).

A copy of the IEC/IRB approval will be sent to Dompé along with relevant correspondence with the IEC/IRB, a roster of IEC/IRB members or the US Department of Health and Human Services (DHHS) general assurance number.

The study will not be started until full written approval has been obtained from the appropriate IEC/IRB. The letter of approval should be dated, and should specify the type (e.g. protocol number) and the date of the documents which were reviewed and approved.

The CRO appointed by Dompé or the PI will submit any future amendment to the protocol to the IEC/IRB which granted the original approval. Any amendment will be implemented only when full approval has been obtained from the appropriate IEC/IRB, except for those amendments which involve only logistical or administrative aspects of the study.

The CRO appointed by Dompé or the PI will send to the IEC/IRB any updated Investigator's Brochure.

The CRO appointed by Dompé or the PI will also submit to the IEC/IRB which approved the protocol, at least annually, any required progress reports and study update, and will inform the IEC/IRB of the termination of the study.

The CRO appointed by Dompé or the PI will report to the IEC/IRB any serious ADRs, life-threatening problems or deaths occurred in other clinical studies conducted with ladarixin.

10.2. ETHICAL CONDUCT OF THE STUDY

This study will be conducted in compliance with the protocol and consistent with FDA and current Good Clinical Practices (GCP), adopting the principles of the Declaration of Helsinki, and all applicable regulatory requirements (ICH E6, 45CFR46, and FDA 21CFR sections 11, 50, 56, 312).

Prior to study initiation, the protocol and the informed consent documents will be reviewed and approved by the IEC/IRB. Any amendments to the protocol or consent materials must also be approved before they are implemented.

10.3. PATIENT INFORMATION AND CONSENT

No study-related procedures (including non-invasive and diagnostic procedures) will be undertaken prior to completion of the consenting process.

Each potentially eligible patient will be informed of the study's objectives and overall requirements. The Investigator or delegate personnel according to site procedures, will explain the study fully to him/her using the ICF. Although patients will be informed that they can withdraw consent at any time, the Investigator will also emphasize that missing data diminish the scientific value of all patients' contributions. Similarly, patients will be informed that safety data might have to be collected after their participation in the study has been completed. If the patient is willing to participate in the study, (s)he will be requested to give written informed consent after being given sufficient time to consider his/her participation and the opportunity to ask for further details.

The ICF will be signed and personally dated by **both** the patient and the Investigator or delegate personnel according to site procedures. A copy of the signed form will be provided to the patient, and the original signed ICF will be retained and filed in the Investigator Site File. Patient consent will be documented in the hospital records.

Individual (i.e. site specific; local language) ICFs will be provided to the site once approved by the IEC/IRB. Any changes requested by the IEC/IRB must be approved by Dompé prior to the documents being used.

10.4. CONFIDENTIALITY

All information obtained during the conduct of the study will be regarded as confidential. Only the minimum necessary information to complete this research trial will be shared with the Sponsor and always in a de-identified manner compliant with HIPAA expectations. An agreement for disclosure will be obtained in writing by the patient and will be included in the ICF. Patient's data collected during (or after completion of) the study will be handled in accordance with applicable USA data protection laws, HIPAA regulations, and European data protection Regulation (EU) No. 679/2016 of the European Parliament and of the European Council regarding the protection of natural person's personal data and the free circulation of said data (hereinafter GDPR EU No. 679/2016) and according the standards of Good Clinical Practice (Law Decree 211/2003).

On the eCRF patients will be identified ONLY by the assigned patient number. If patient names are included on copies of documents submitted to Dompé or the CRO appointed by Dompé, the names will be obliterated or masked and the assigned patient number added to the document.

The Investigator should keep a separate log (Patient Master List) of patient's codes, names and addresses.

The secondary use of personal data

Personal Data will be processed for the purpose of conducting any further analysis to generate new scientific hypotheses that could be verified through new research. This further analysis of personal data ("the secondary use of personal data") may deviate from this protocol and, for this reason, it may require a new clinical trial (and therefore a new legal basis for processing patient's personal data).

If the further analysis does not deviate from this protocol, there is no need to change the legal basis since the secondary use is considered to be compatible with the primary use.

Analyses of subcategories of data, for example, may be conducted consistent with the primary use.

The secondary use of data may be the subject of scientific and/or statistical publications.

